9.3.7. Analysis of Bleeding Profiles

Bleeding profile categories will be determined based on the amount of bleeding experienced by patients as reported in the eDiary. When a patient is menstruating, the amount of bleeding during the past 24 hours is captured daily in the eDiary with five response options: spotting, light, moderate, heavy, and extremely heavy. It will be assumed that there is no bleeding on days that the patient either uses the eDiary and reports that she is not menstruating, or when the patient misses reporting menstruating within eDiary cycle. The responses to the eDiary question about the amount of bleeding will be used to define the bleeding profile categories (Table 25).

After Week 52, to reduce patient burden, eDiary data were collected over four eDiary collection cycles on the following schedule: Week 57 to the Week 65 visit, Week 71 to the Week 78 visit, Week 85 to the Week 91 visit, and Week 98 to the Week 104 visit. After the Week 104 visit, patients continued daily eDiary entry until the 30-day Follow-Up visit.

Table 25: Definitions of Bleeding Profile Categories

Bleeding Profile Category	Category Definition
Irregular bleeding	3 to 5 bleeding/spotting episodes and less than 3 bleeding-free intervals of least 14 days during a bleeding-profile period
Prolonged bleeding	Bleeding/spotting episodes of more than 14 days during a bleeding-profile period
Frequent bleeding	More than 5 bleeding/spotting episodes during a bleeding-profile period
Infrequent bleeding	1 or 2 bleeding/spotting episodes during a bleeding-profile period
No bleeding	No bleeding during a bleeding-profile period
Normal bleeding	None of the above definitions are met

^a Bleeding/spotting episode: at least one day with bleeding or spotting reported, bounded by bleeding-free intervals.

^b Bleeding-free interval: at least two consecutive days with no bleeding or spotting reported, bounded by bleeding/spotting episodes.

The number and percentage of patients belonging to each of the bleeding profile categories defined in Table 25 will be summarized by pivotal phase 3 study treatment group over four bleeding-profile periods: Days 1 through 90, Day 91-Day 180, Day 181-Day 270, and Day 271-365. A patient must have at least 90 days of treatment exposure to be included in the summary of each period. No analyses of bleeding profile after Day 365 will be performed because all of the eDiary reporting cycles are less than 90 consecutive days.

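### Table 25 footnotes: a woman who bleeds without a two-day break has no countable episode and falls into Normal bleeding; the boundary rule for bleeds at a period edge is not stated

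*SAP*

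**What the plan says.** SAP Section 9.3.7 sorts each patient into a bleeding category in four periods: Days 1-90, 91-180, 181-270 and 271-365. Table 25 defines the categories:

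- Irregular: "3 to 5 bleeding/spotting episodes and less than 3 bleeding-free intervals of least 14 days during a bleeding-profile period"
- Prolonged: "Bleeding/spotting episodes of more than 14 days during a bleeding-profile period"
- Frequent: "More than 5 bleeding/spotting episodes during a bleeding-profile period"
- Infrequent: "1 or 2 bleeding/spotting episodes during a bleeding-profile period"
- No bleeding: "No bleeding during a bleeding-profile period"
- Normal: "None of the above definitions are met"

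Footnote a defines an episode as "at least one day with bleeding or spotting reported, bounded by bleeding-free intervals". Footnote b defines a bleeding-free interval as "at least two consecutive days with no bleeding or spotting reported, bounded by bleeding/spotting episodes". Diary days with no report are taken as days without bleeding. The section gives no rule for a bleed cut by a period boundary. It does not say whether the bounding intervals must lie inside the period, whether the categories are exclusive, or which one prevails.

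**The concern.** Four of the six categories need at least one episode, and an episode needs a dry interval on each side. The longest bleeds are the least likely to have those dry intervals. Because Normal is whatever remains, a bleed that fails the episode definition is not flagged or left unclassified. It is counted in the most reassuring row. Table 25 is where this section counts women with prolonged bleeding, so that count could be too low and Normal too high for the pattern of most clinical interest.

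A second problem is reproducibility. Since the text is silent on period edges, two programmers could follow it faithfully and produce different tables from the same diaries.

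**Working it through.** The SAP states no figure here to reproduce. The check applies Table 25 to constructed diaries covering Days 1-365.

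**Inputs (Section 9.3.7).** An episode is at least 1 bleeding day with a bleeding-free interval on each side. An interval is at least 2 dry days. Prolonged means an episode of more than 14 days; Infrequent means 1 or 2 episodes; Normal is the residual.

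**Readings compared**

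- A: footnote a is enforced with bounds inside the period; any gap of at least 2 days counts as an interval.
- B: footnotes a and b are both enforced inside the period.
- C: footnote a is enforced, but bounds may lie outside the period, within Days 1-365.
- D: the proposed fix, in which a period edge counts as a bound.

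**Results**

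| Bleeding pattern | Period assessed | A | B | C | D |
|---|---|---|---|---|---|
| Every day, 1-365 | 91-180 | Normal | Normal | Normal | Prolonged + Infrequent |
| Days 85-200 only | 91-180 | Normal | Normal | Prolonged + Infrequent | Prolonged + Infrequent |
| Days 91-110 only | 91-180 | Normal | Normal | Prolonged + Infrequent | Prolonged + Infrequent |
| Days 1-5 only | 1-90 | Normal | Normal | Normal | Infrequent |
| Days 86-90 only | 1-90 | Normal | Normal | Infrequent | Infrequent |
| Days 91-95 and 120-124 | 91-180 | Infrequent | Normal | Infrequent | Infrequent |
| Days 91-95 and 120-139 | 91-180 | Prolonged + Infrequent | Normal | Prolonged + Infrequent | Prolonged + Infrequent |
| Days 91-95, 130-134, 176-180 | 91-180 | Infrequent | Normal | Irregular | Irregular |
| Days 130-134 only | 91-180 | Infrequent | Normal | Infrequent | Infrequent |

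**What follows**

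1. Uninterrupted bleeding over Days 1-365 gives 0 episodes, hence Normal, under A, B and C. Single dry days do not change this, because an interval needs two.
2. A sole bleed on Days 1-20 (20 days) or Days 60-90 (90 - 60 + 1 = 31 days) exceeds 14 days but gives 0 episodes under A, hence Normal. Under C, Days 60-90 is Prolonged if dry days follow Day 90. Under D both are Prolonged.
3. An edge bleed together with another bounded episode is never Normal under A. It can still be misclassified, as the three-bleed row shows (Infrequent where D gives Irregular).
4. Under B nobody who bleeds has an episode, even with one mid-period bleed. The first run in a period has nothing on its outer side, so it is not valid; its neighbour then loses a bound, and so on along the whole period.

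**Regular menses, reading A against D.** Every cycle phase over a 90-day period was enumerated, treating dry runs cut by the period edge as intervals.

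| Cycle / bleed length (days) | Episode count changes | Infrequent, A to D | Normal, A to D |
|---|---|---|---|
| 28 / 5 | 10/28 = 36% | 2/28 = 7% to 0% | 26/28 = 93% to 100% |
| 28 / 7 | 12/28 = 43% | 4/28 = 14% to 0% | 24/28 = 86% to 100% |
| 30 / 5 | 8/30 = 27% | 8/30 = 27% to 0% | 20/30 = 67% to 28/30 = 93% |

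These are shares of cycle phases in constructed patterns, not expected trial frequencies.

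**The case against.** The strongest reply is that the footnotes are loosely worded and a sensible programmer would not apply them literally. Reading B supports this: full strictness leaves no episode for any woman, so it cannot be what was meant. That stands as a comment on intent. It does not settle what will be programmed, because the text supplies no workable alternative.

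A reader might infer that any bleed touching a period edge is called Normal. The SAP does not support that. It never says the bounds must lie inside the period, the periods are contiguous, and Section 7.2.4 has the eDiary completed daily until Week 52, so the neighbouring days are recorded. Even a Day 1 bleed might be bounded by diary days from the pre-treatment baseline assessment period. Nor is a long bleed crossing a boundary necessarily missed as Prolonged in both periods; that needs the within-period reading, or bleeding that never stops.

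A reader might also take the 36%, 43% and 27% as the size of the safety problem. They are not. They concern regular menses under reading A, where the misplaced women go to Infrequent, not Normal.

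Long bleeding also shows elsewhere. Table 26 reports bleeding days per 28-day window, Section 9.1.7 summarizes uterine-bleeding adverse events, and two consecutive unreported days would supply a bound. This limits the harm but does not remove it: Table 26 gives means, medians and extremes, not the number of women with prolonged bleeding.

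**Conclusion.** The point holds for bleeding with no two-day gap. Such a woman has zero episodes and is counted as Normal under every reading of the text tested, taking Days 1-365 as the diary. For bleeds at a period edge it holds conditionally: the result is Normal only if bounds must lie inside the period and the woman has no other bounded episode, or if the bleed sits at an end of the diary and no days beyond it are used. The circularity of footnotes a and b is a defect in its own right.

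The number of patients affected cannot be derived from the SAP, which gives no frequency of uninterrupted bleeding. The consequence is limited to one descriptive safety table; no efficacy endpoint depends on it. It should be corrected because a stated rule places the most abnormal pattern in the most reassuring category.

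**What to change.** Amend both footnotes so that the start and end of the bleeding-profile period count as bounds. Any run of bleeding or spotting days separated from other runs by at least two dry days is then one episode, and any dry run of at least two days is an interval. This also removes the circularity.

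Add two statements to Section 9.3.7:

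- How a bleed crossing a period boundary is assigned, and how its length is measured for Prolonged, using the adjacent eDiary days.
- Whether the categories are exclusive and, if so, which takes precedence, since one long bleed meets both Prolonged and Infrequent.

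No minimum episode count for Normal is needed: once edges count, every woman who bleeds has at least one episode, and one or two already means Infrequent.

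The cost is a footnote revision and a programming change on data already collected. Uninterrupted bleeding moves from Normal to Prolonged. For regular menses Normal may become more common, as the second table in the working shows.

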Summaries of bleeding intensity and number of bleeding days based on 28-day intervals will be provided from the last 28 days starting from the pivotal phase 3 baseline through Day Day 731. The following 28-day windows will be used for summaries of bleeding during the randomized treatment period: Week 4 (Days 1 through 28), Week 8 (Days 29 through 56), Week 12 (Days 57 through 84), Week 16 (Days 85 through 112), Week 20 (Days 113 through 140), Week 24 (Days 141 through 168), Week 28 (Days 169 through 196), Week 32 (Days 197 through 224), Week 36 (Days 225 through 252), Week 40 (Days 253 through 280), Week 44 (Days 281 through 308), Week 48 (Days 309 through 336), Week 52 (Days 338 through 365), Week 65

(Days 429 through 456), Week 78 (Days 520 through 547), Week 91 (Days 611 through 638) and Week 104 (Days 704 through 731). Only patients who were on study drug for all days in a given 28-day window will be included in the summary for that window. The specific summaries of bleeding that will be provided are described in Table 26.

Table 26: Summaries of Bleeding Amount and Number of Bleeding Days

Bleeding outcome	Type of summary
Bleeding amount (or intensity), defined numerically as: Spotting = 1 Light = 2 Moderate = 3 Heavy = 4 Extremely Heavy = 5	Mean, SD, median, minimum, maximum; based on all eligible patients who report bleeding in the eDiary.
Number of bleeding days	Mean, SD, median, minimum, maximum; based on all eligible patients, regardless of whether any bleeding is reported in the eDiary.
Number of bleeding days by the following bleeding amount (or intensity) categories: No bleeding Spotting Light Moderate Heavy Extremely Heavy	Mean number of days per category.

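### The fourth bleeding-profile period is 95 days against 90 for the other three, with unscaled category cut-offs, so its category shares can shift without any change in bleeding

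*SAP*

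**What the plan says.** SAP section 9.3.7 reports the number and percentage of women in each bleeding-profile category, by pivotal-study treatment group, over four periods: "Days 1 through 90, Day 91-Day 180, Day 181-Day 270, and Day 271-365".

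Table 25 sets the categories by absolute counts within a period:
- No bleeding: "No bleeding during a bleeding-profile period"
- Infrequent: "1 or 2 bleeding/spotting episodes during a bleeding-profile period"
- Irregular: "3 to 5 bleeding/spotting episodes and less than 3 bleeding-free intervals of least 14 days during a bleeding-profile period"
- Frequent: "More than 5 bleeding/spotting episodes during a bleeding-profile period"
- Prolonged depends on episode length, and Normal is what remains.

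Inclusion has one rule for all four periods: "A patient must have at least 90 days of treatment exposure to be included in the summary of each period". The section stops at one year for this reason: "No analyses of bleeding profile after Day 365 will be performed because all of the eDiary reporting cycles are less than 90 consecutive days". The last two statements show that 90 days is the working reference length.

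Neighbouring tables keep their window length at the same boundary. The 28-day summaries in section 9.3.7 use "Week 52 (Days 338 through 365") after a Week 48 window that ends on Day 336. The 56-day amenorrhea windows in section 9.3.8 end with Days 310 to 365. The SAP gives no reason for the longer fourth bleeding-profile period.

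**The concern.** A longer window catches at least as many episodes of the same bleeding pattern. If the cut-offs stay fixed while the window grows, some women change category only because they were watched for five more days. The four periods are consecutive and will be read in order, so the step from the third to the fourth can mix window length with real change on treatment.

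The exposure rule adds a smaller problem. It asks for 90 days whatever the length of the period and does not say where those days must fall. If it is read as 90 days within the period, a woman with 90 to 94 days enters the 95-day period. Observed length then also differs between women inside that period.

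What is at stake is the reading of the last step in one safety table. No test, and no primary or secondary efficacy endpoint, depends on it.

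**Working it through.** **Lengths** (section 9.3.7; end − start + 1)
- 90 − 1 + 1 = 90
- 180 − 91 + 1 = 90
- 270 − 181 + 1 = 90
- 365 − 271 + 1 = 95, which is 5/90 = 5.6% longer
- For contrast, 28-day table at Week 52: 365 − 338 + 1 = 28 (Day 337 is left out)
- For contrast, 56-day table at Week 52: 365 − 310 + 1 = 56 (the start moves one day later than the 28-day step from Day 281 would give)

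**Direction.** Adding days to a window cannot remove or merge episodes already seen in it. The episode count can only rise or stay equal. So No bleeding can only fall or stay equal, and more than five episodes can only rise or stay equal. The middle categories gain women from below and lose them above, so they can go either way.

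**Size with sporadic bleeding.** The rates are assumptions. Episode counts are taken as Poisson with mean m in 90 days and m × 95/90 in 95 days, sorted into the Table 25 count bands. For m = 1, no bleeding is exp(−1) = 36.8% against exp(−95/90) = 34.8%.

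Change from 90 to 95 days, in percentage points:

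| m per 90 days | 0 episodes | 1–2 | 3–5 | more than 5 |
|---|---|---|---|---|
| 0.25 | −1.1 | +1.0 | 0.0 | 0.0 |
| 0.5 | −1.7 | +1.4 | +0.2 | 0.0 |
| 1 | −2.0 | +0.9 | +1.0 | 0.0 |
| 3 | −0.8 | −2.9 | +1.9 | +1.8 |
| 5 | −0.2 | −2.0 | −2.7 | +4.9 |

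**Size with regular cycles.** The assumptions are 5-day bleeds, every start offset equally likely, and any bleed that touches the window counted as an episode. The mean number of episodes is then (L + 4)/cycle length.
- 35-day cycles: 94/35 = 2.69 against 99/35 = 2.83. Women have two or three episodes. The share with two (Infrequent) is 11/35 = 31.4% in 90 days and 6/35 = 17.1% in 95 days.
- 28-day cycles: 94/28 = 3.36 against 99/28 = 3.54. The share with four rather than three episodes is 10/28 = 35.7% against 15/28 = 53.6%. Both counts lie in the 3-to-5 band, so a category changes only through the interval clause. Footnote b of Table 25, read literally, counts only intervals bounded by episodes. Three episodes then give two intervals (Irregular) and four give three (Normal), so Irregular falls from 64.3% to 46.4%. If intervals at the edges of the period also count, the change is 0 for exact cycles and about 3 points when cycle length has an SD of 3 days (simulated Irregular 3.6% to 0.4%).

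**With a 90-day fourth period** all four lengths are equal, and the expected shares at a constant bleeding rate are identical.

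**The case against.** The case for leaving the table alone has real substance.

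- The analysis is descriptive. Sections 4.1 and 7.1 plan no formal comparisons, and the SAP names no contrast between the third and fourth periods. This stands, and it is why the point is minor.
- All three treatment groups have the same periods. A reader might infer that the extra days distort group comparisons, but the documents do not support that: within a period every group has the same window.
- Time trends in bleeding also appear in equal-length windows: the 28-day bleeding summaries, and the 28-day and 56-day amenorrhea rates. This softens the consequence, although those tables do not report the Table 25 categories.
- Regular cycling is a doubtful model for the third and fourth periods, when all women take open-label relugolix with E2/NETA. The only cycle length the SAP mentions is 28 days (section 7.2.6), not 35. The 31% to 17% figure is therefore an illustration for cycling women and does not estimate the effect on the whole table.
- Day 365 is the Week 52 target day (section 4.3.8, Table 3), so running the last period up to it is a plausible choice. The SAP does not say so, and a 90-day period can also end on Day 365.

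A reader might also infer that Infrequent is biased downward in general. It is not. At one episode per 90 days the share with 1 or 2 episodes rises from 55.2% to 56.1%, and it rises at the lower rates shown too. Nor does the 28-day-cycle result show a category shift on every reading, since it depends on footnote b being taken literally.

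**Conclusion.** The unequal length follows directly from the SAP's own day bounds, and nothing in section 9.3.7 adjusts the cut-offs for it. Only two directions are certain at an unchanged bleeding rate: No bleeding cannot rise, and more than five episodes cannot increase less than zero, that is, cannot fall. Infrequent, Irregular and Normal have no fixed direction.

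The size rests wholly on assumed bleeding rates. It is about 1 to 2 points for sporadic bleeding of 0.25 to 1 episode per 90 days, and more for women who still cycle regularly. Women with sustained amenorrhea do not contribute, so the effect on a whole group is probably small. The artefact is confined to comparing the fourth period with earlier ones. This is a small defect in a descriptive safety table, worth correcting because the correction is almost free.

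**What to change.** In section 9.3.7, make the fourth period 90 days. Day 271 to Day 360 keeps it contiguous with the third period. Day 276 to Day 365 ends it at Week 52 and leaves Days 271 to 275 out, much as the 28-day table leaves out Day 337.

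In the same paragraph, state that the 90 days of treatment exposure must fall within the period being summarised. With every period at 90 days this already means exposure on each day of the period, so no further inclusion rule is needed.

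The cost is two changes of SAP wording and five diary days unused in this one table. A footnote giving the reason for 95 days would warn the reader but would leave the artefact in place.

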Patients would have received their last dose of study drug in the pivotal phase 3 study on the day prior to the Week 24/Baseline visit and will receive their first dose of study drug for this extension study in the clinic after the patient is determined to be eligible for this extension study and has provided informed consent to participate. Therefore, results of testing required for eligibility must be available on or prior to the Week 24/Baseline visit. The administration of the first dose of study drug for MVT-601-3103 will define enrollment into this study. Patients will then take the open-label study treatment (relugolix 40 mg co-administered with estradiol 1 mg and norethindrone acetate 0.5 mg) orally once daily for 80 weeks. If necessary, for logistical reasons (eg, delayed availability of study drug supply on site, others), and with sponsor/designee approval, the first dose of open label study drug for MVT-601-3103 may be administered up to 10 days following the pivotal phase 3 study Week 24/Baseline visit. If the first dose of study drug is not given during this up to 10-day interval, the pivotal phase 3 study safety follow-up procedures should be followed (ie, adverse event reporting, electronic diary [eDiary] completion, etc.).

During the 80-week Open-Label Treatment period and the ~30-day Follow-Up period, patients will continue to record study treatment, assessment of pain using the NRS, menstrual bleeding, analgesic use, and the functional effects of endometriosis-associated pain (sB&B) in the eDiary during the time periods specified in the protocol. Only study-specific rescue analgesic medications should be used starting with the Week 24/Baseline visit and through the Follow-Up visit and these medications will be taken for control of pain and not prophylactically. Health-related quality of life questionnaires; PGIC for dysmenorrhea, NMPP, and dyspareunia; and PGA for pain and function will be completed during the visits on an electronic tablet, according to the study protocol Schedule of Activities (Section 1.1).

Safety will be assessed throughout the study by monitoring adverse events, vital signs and weight, physical examinations, clinical laboratory tests, 12-lead ECGs, mammograms (for women who are or become ≥ 40 years old during the study), endometrial biopsies, and bone mineral density with DXA.

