4.3.3. Study Day

Study day will be calculated with respect to the date of the first dose of study drug in the pivotal phase 3 study (Study Day 1). For assessments conducted on or after the date of the first dose of pivotal phase 3 study drug, study day will be calculated as:

$$(\text{Assessment date} - \text{date of first dose of pivotal phase 3 study drug}) + 1$$

For assessments conducted before the date (and time) of the first dose of pivotal phase 3 study drug, study day will be calculated as:

$$(\text{Assessment date} - \text{date of first dose of pivotal phase 3 study drug})$$

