5. STUDY POPULATION

5.1. Subject Disposition

The number and percentage of patients for each of the following categories will be summarized by pivotal phase 3 study treatment group in final analysis:

- All patients enrolled defined as taking the first dose of study drug in the Extension Study;
- Patients included in the Extension Study population;
- Patients included in the Extension Safety population.

In final analysis, the number and percentage of patients for each of the following categories will be summarized by pivotal phase 3 study treatment group:

- Patients who completed 52 weeks treatment (24 weeks pivotal study treatment period and 28 weeks open-label treatment period)
- Patients who completed the 104 weeks of treatment (24 weeks pivotal study treatment period and 80 weeks open-label treatment period);

- Patients who discontinued early from the 80 weeks open-label treatment period and reasons for discontinuation;
- Patients who entered the BMD post-treatment Follow-Up period.

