9.3.8. Amenorrhea Rate and Sustained Amenorrhea Rate

Determination of amenorrhea will be based on a patient's daily menstruation status as reported in the eDiary. Amenorrhea for at least 56 consecutive days is defined as the lack of bleeding for at least 56 consecutive days after starting randomized study treatment in pivotal phase 3 study until Week 52. Amenorrhea for at least 28 consecutive days is defined as the lack of bleeding for at least 28 consecutive days after starting randomized study treatment in pivotal phase 3 study until Week 104. The study day when amenorrhea begins is defined as the first study day following the last reported day of menstruation. It will be assumed that there is no menstruation on days when menstrual status is not reported in the eDiary.

A summary of amenorrhea for at least 56 consecutive days will be provided by pivotal phase 3 study treatment group based on the following 56-day time intervals from pivotal phase 3 baseline through Day 365: Week 8 (Days 1 through 56), Week 12 (Days 29 through 84), Week 16 (Days 57 through 112), Week 20 (Days 85 through 140), Week 24 (Days 113 through 168), Week 28 (Day 141 through 196), Week 32 (Day 169 through 224), Week 36 (Day 197 through 252), Week 40 (Day 225 through 280), Week 44 (Day 253 through 308), Week 48 (Day 281 through 336), and Week 52 (Day 310 through 365). No analyses of 56-day amenorrhea after

Week 52 will be performed because some eDiary reporting cycles are less than 56 days. A summary of amenorrhea for at least 28 consecutive days intervals from pivotal study baseline through Day 731 will be provided by pivotal phase 3 study treatment group. The number and percentage of patients who are amenorrheic (ie, the amenorrhea rate) in each time interval will be presented. In each time interval, the numerator for the amenorrhea rate is the number of patients who did not bleed during the time interval; the denominator is the number of patients who remained on treatment during the entire time interval.

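### The Week 104 bleeding window (Days 704-731, study drug required on every day) runs three days past the planned last dose on Day 728, so women who finish exactly on schedule drop out of that summary

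*SAP*

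**What the plan says.** Section 9.3.7 lists 28-day windows for bleeding amount and number of bleeding days. The last window, followed directly by the eligibility rule that applies to every window, reads: "Week 104 (Days 704 through 731). Only patients who were on study drug for all days in a given 28-day window will be included".

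Section 9.3.8 plans a 28-day amenorrhea summary through Day 731. For each interval, "the denominator is the number of patients who remained on treatment during the entire time interval". It lists the 56-day intervals one by one but not the 28-day ones.

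Four other statements fix the calendar:
- Section 4.3.3: study day is "calculated with respect to the date of the first dose of study drug in the pivotal phase 3 study (Study Day 1").
- Section 2.1: women take their "last dose of study drug in the pivotal phase 3 study on the day prior to the Week 24/Baseline visit". The first extension dose is given in clinic once eligibility and consent are settled, or up to 10 days after that visit for logistical reasons with approval. Open-label treatment is then taken "orally once daily for 80 weeks".
- Section 5.1 counts as completers "Patients who completed the 104 weeks of treatment (24 weeks pivotal study treatment period and 80 weeks open-label treatment period").
- Section 4.3.8, Table 3: target day 169 for Week 24 and 731 for Week 104.

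**The concern.** Earlier bleeding windows can end a day late without harm, because treatment continues beyond them. Week 104 is the one window that ends at the planned end of treatment. If its last day falls after the planned last dose, the all-days-on-drug rule removes women for keeping to the schedule, although Section 5.1 counts them as completers.

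At stake is who the two-year bleeding results describe. Inclusion at Week 104 would depend on a late extension start or a late final visit. The number of women would fall at that timepoint for a reason unrelated to discontinuation, and a reader of the table could not tell the two apart.

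**Working it through.** **Inputs from the SAP.** Day 1 is the first pivotal dose (4.3.3). The pivotal period is 24 weeks and the extension 80 weeks, dosed daily (2.1, 5.1). The last pivotal dose is the day before the Week 24 visit (2.1), whose target is Day 169 (Table 3). The Week 104 window is Days 704-731 (9.3.7).

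**Checking Day 731 against the SAP's pattern.** All 16 Table 3 target days from Week 4 to Week 91 equal 7 × week + 1, for example 7 × 52 + 1 = 365 and 7 × 91 + 1 = 638. Week 104 would give 7 × 104 + 1 = 729; Table 3 prints 731. Bleeding windows end at 7 × week for Weeks 4-48 and at 7 × week + 1 for Weeks 52-91. Week 104 ends at 7 × week + 3. The window is 28 days long (731 − 704 + 1 = 28); only its position is off.

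**Planned last dose.**
- Last pivotal dose: 24 × 7 = Day 168.
- First extension dose, no delay: Day 169.
- Last extension dose: 169 + 80 × 7 − 1 = Day 728.
- Overrun: 731 − 728 = 3 days (Days 729, 730 and 731 off drug).

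**Effect of a delayed first extension dose, with exactly 80 weeks of dosing.** Last dose = 728 + delay.

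| Delay (days) | Last dose | Meets the rule for Days 704-731? |
|---|---|---|
| 0 | 728 | No |
| 1 | 729 | No |
| 2 | 730 | No |
| 3 to 10 | 731 to 738 | Yes |

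**A woman seen on Table 3's own target, Day 731.** If her last dose is the day before the visit (assumption), it falls on Day 730 and she misses by one day. If she also doses on Day 731, she is included.

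**Illustrative size.** The SAP gives no distribution of final-visit or last-dose days. Assume visit days are normal with SD 3 to 7 days. If the last dose is the day before the visit, inclusion needs a visit on Day 732 or later, so the share retained is 1 − Φ((731.5 − centre)/SD). If a dose is taken on the visit day, the cut is 730.5. Example: centre 729, SD 3, dose the day before gives 1 − Φ(2.5/3) = 20% retained, 80% lost.

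| Centre of visit days | Lost, last dose the day before | Lost, dose on visit day |
|---|---|---|
| 729 (7 × 104 + 1) | 64-80% | 58-69% |
| 731 (Table 3 target) | 53-57% | 43-47% |
| 734 (731 plus a three-day later start) | 20-36% | 12-31% |

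**Candidate windows for a last dose on Day 728.** Days 701-728 keep her. Days 702-729, the Week 52-91 pattern, still exclude her by one day. Days 704-731 exclude her by three.

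**The case against.** The strongest reply is that Day 728 is printed nowhere, whereas Day 731 is the SAP's Week 104 target in seven visit-window tables (Tables 3, 4, 5, 6, 7, 9 and 10). The bleeding windows for Weeks 52, 65, 78 and 91 also end on their Table 3 target days, so the Week 104 window follows a consistent convention. For a woman seen on Day 731 the shortfall is one day, or none if she doses that day. The SAP states last-dose timing for the Week 24 visit only; for Week 104 it may be in the protocol, which is not at hand. Late extension starts, whether from a late Week 24 visit or the permitted 10-day delay, push the last dose beyond Day 728.

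This stands as a limit on size. A reader might infer that most completers, some 60-80%, are lost. That figure requires visits centred on Day 729, which is not the SAP's target, and it ignores late starts. Nor does the SAP show that those who remain would be few or would bleed differently: nothing in it links finishing a few days late to bleeding. The extension to Section 9.3.8 is also partly inference, since the 28-day intervals there are not listed.

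The reply does not remove the conflict. Following the convention of ending on the target day does not help when the inclusion rule demands drug on a day after the planned 104 weeks have ended.

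**Conclusion.** The conflict holds. From the SAP's own treatment lengths and study-day definition, a woman who takes exactly the planned 104 weeks, or whose first extension dose is one or two days late, cannot enter the Week 104 bleeding-amount and bleeding-days summaries. One seen on the Day 731 target misses by one day if her last dose is the day before, which is an assumption. The 28-day amenorrhea rate shares the fault only if its last interval is also Days 704-731.

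How many women are lost cannot be determined from the SAP. Under the assumed normal model the loss is about 20% to 80% when the last dose is the day before the visit, and about 12% to 69% when a dose is taken on the visit day. These are illustrations of sensitivity, not estimates.

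The consequence is confined to one timepoint of descriptive safety summaries, with no formal comparisons planned. The primary Week 104/EOT responder endpoint is anchored on the date of last dose (Section 7.2.4 and Table 11) and is unaffected. The correction should still be made: the rule works against the women it is meant to describe, and it is easy to repair.

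**What to change.** In Section 9.3.7, redefine the Week 104 28-day window in one of two ways:
- Days 701-728; or
- for women who completed Week 104, the 28 days ending on the date of last dose, restricted to eDiary collection days. This matches the anchor that Table 11 already uses for Week 104/EOT.

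Days 701-728 lie inside the last eDiary cycle as Table 11 defines it: with the Day 731 target, its Week 104 row starts at 731 − 51 = Day 680.

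In Section 9.3.8, state the 28-day intervals explicitly and use the same Week 104 window. Report the number of Week 104 completers beside the number included, so that any remaining exclusions are visible.

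The Day 731 target in the visit-window tables need not change for this purpose. Table 3's Week 104 window, for instance, runs from Day 685 to six days after last dose, so a two-day shift of target would rarely matter. The cost is a short text change in two sections and one derivation parameter. Dosing and data collection are untouched.
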